Study Title:

Using 'Guided-Discovery-Learning' to optimize and maximize transfer of surgical simulation

Internal Short title: GDL-Efficacy
Ethics Ref: H-18041917

NCT: 03684720

Acronym: GDLEFFICACY

Date and Version No: 19.09.2018, vs.0.2

Chief Investigator:

[name], Bach. Med¹

Investigators:

[name] PhD,²

[name],³

[name], MD, Professor¹

[name] MSc. PhD³

[name] PhD,³

Sponsors:

Copenhagen Academy for Medical Education and Simulation, Capital Region, Denmark

Funder:

Application for funding is ongoing.

1. Copenhagen Academy of Medical Education and Simulation, Rigshospitalet; Copenhagen, Denmark.

2. Department of Gynecology and Obstetrics, Hvidovre Hospital, Region H, Zealand, Denmark

3. The Wilson Centre, University Health Network and University of Toronto; Toronto, Ontario

Investigators [name], [name], [name], [name], [name] and [name] have no conflict of interest or financial ties to disclose.

The reporting this study will conform to the CONSORT statement.

Confidentiality Statement

This document contains confidential information that, prior to trial registration at www.clinicaltrials.gov, must not be disclosed to anyone other than the Sponsor, the Investigator Team, host organization, and members of the Research Ethics Committee, unless authorized to do so.

Table of Contents

1. Synopsis	3
2. Abbreviations	3
3. Background and Rationale	3
4. Objective and Outcome Measure.....	6
5. Study Design	6
6. Participant identification	8
7. Study Procedures.....	8
8. Statistics and Analysis	10
9. Data management	11
10. Ethical and Regulatory Consideration.....	11
11. Finance	12
12. Publication Policy	12
13. Appendix A.....	13
14. Appendix B.....	14
15. Appendix C.....	15
16. Appendix D.....	16
17. Appendix E.....	17
18. Appendix F	18
19. Appendix G.....	19
20. References.....	20

1. Synopsis

Study Title	Using 'Guided-Discovery-Learning' to optimize and maximize transfer of surgical simulation
Research Objective	To explore the effect of guided-discovery-learning in transfer of surgical skills
Study Design	A prospective randomized study and explorative study
Study Participants	Students from the Medical Faculty who have not received suture-training
Planned Sample Size	Sixty-four participants
Planned Study Period	Twenty-four months
Objectives	To explore the effect of guided-discovery-learning vs traditional instructor lead teaching in the transfer of basic surgical skills.

2. Abbreviations

CI	Chief Investigator
ICF	Informed Consent Form
RREC	Regional Research Ethics Committee
ST	Surgical Teacher
OSATS	Objective Structured Assessment of Technical Skill
CAMES	Copenhagen Academy for Medical Education and Simulation

3. Background and Rationale

Technical skills are a core competency in surgical specialties. The level of technical skills is directly linked to patient outcomes and it is an absolute requirement that surgical trainees learn to master basic surgical skills. It is therefore a necessity that medical students also become well equipped with these skills, such as suturing. During the last decade, minimally invasive techniques have made their way to the operating room and improved patient outcomes. Despite these advances it is still necessary for surgeons to master the open surgical skills. Unexpected complication can arise in minimally invasive procedures that require conversion to open access surgery. Furthermore, there are procedures where you cannot use minimally invasive techniques. Because of the extensive use of minimally invasive surgery, it is becoming more difficult for doctors as well as medical students in surgical departments to gain the level of experience needed, to become proficient in open surgical techniques. Pre-clinical teaching and simulation training is a possible solution to this problem.¹ For novice learners, simulation training is an opportunity to acquire fundamental skills such as suturing in a safe and high-feedback environment and without the difficulties of acquiring these skills in the workplace². For more advanced trainees, simulation affords the practice of difficult and complex procedures which may be otherwise too unsafe to acquire during patient care. But, merely implementing simulation training is no guarantee of

educational utility, and instead thoughtful curricular integration of simulation requires considering the role and purpose of the simulator, the student experience, debriefing, and the intended outcomes to evaluate success.^{3,4}

One potential area for optimizing simulation-based training is to clarify instructors' roles when providing guidance and direct supervision. One of the challenges with simulation training is the amount of resources this sort of education requires. Especially the amount of time a student spends interacting with an instructor. Supervision and instruction are key to an effective simulation-based training, and there is mounting evidence, which suggest, that we need to reconsider the balance between instruction and discovery, allowing for a good interaction between student and teacher, encouraging learning^{5,6} Therefore the question is; on what level should simulation-based teaching be instructor-orientated? When teaching technical medical skills, the answer to the question, whether the training should be discovery-orientated or instructor-orientated has been thoroughly researched.⁷ Medical Education literature has long moved away from the question of either or, and is now more focused on, in which order discovery- and instruction-teaching should be, to provide the best learning outcome.^{8,9} Recent studies has shown some positive results of guided-discovery-learning, which in its simple form, combines both elements from discovery and instruction-based teaching.¹⁰ Especially the ability to '*transfer*' learning seems vastly improved, with this teaching method. Transfer tasks faced by learners exist on spectrum with a common challenge being new problems which are more complex or in new contexts but essentially require replication of previously learned skills, i.e. near transfer. While near transfer can be difficult for learners, even more challenging is transfer that requires they apply their previous skills and understanding to learn new skills or concepts, i.e. far transfer. Guided-discovery learning has been shown to especially positively impact this latter type of transfer task^{11,12}. Thus guided-discovery may promote student-autonomy and self-learning which subsequently enables students to take responsibility for their own future learning.^{11,12}

In a pilot-study completed by our research-partners at the Wilson-Centre in Toronto, Canada, they compared groups of *discovery followed by direct discovery* (DD) with *instruction followed by discovery* (IP). In the case of DD, the participants, where given the materials needed to complete a simple suture, and a finished suture to look at. After the discovery-phase, they were parred with an instructor who demonstrated how it was to be performed. In the IP-case they were first instructed on how to perform the suture, and were afterwards allowed to practice it. At the end of the course both groups were given a post-test of ability, and a week-later both groups were given a retention test as well as a transfer test. The pilot-study included 26 participants in total, divided in two groups of 13. The participants were randomized, and everything was filmed and scored by blinded raters after an international standard. There were no significant results for the immediate post-test as well as the retention test. But in the case of the transfer test, the DD-group was far superior.

Our study will expand on the pilot-study to provide a comparison of guided discovery to traditional instruction for the learning of suturing tasks in surgery, seeing if Guided-discovery-learning works in a much larger research group. Using a double randomized, mixed-methods experimental design, we will investigate the effect of discovery followed by direct instruction (DD) vs. instruction followed by practice (IP) for the acquisition and two types of transfer of surgical skills. To understand *how* and *why* guided-discovery learning changes the learning processes of trainees, we will also film and analyze the interactions of a small-subset of participants in each condition as well as conducting focus-group interviews. Using an exploratory approach, we will explore how discovery learning prior to direct instruction might

change participants' interactions with instructors and task compared to their interactions during initial direct instruction. We will seek to uncover which exploratory approach or approaches provide the best qualitative data. This part is elaborated and investigated in a separate additional protocol.

We hypothesize that:

- 1) Participants in the DD condition will be better able to transfer their knowledge to learning a new skill (i.e., preparation for future learning).
- 2) Participants in the DD condition will have equivalent performance to IP on post-test, but a similar or slightly improved performance on transfer of suturing skill to a more complex task (near-transfer).
- 3) Participants in the DD condition will interact differently with instructors and will use their learnings from the discovery phase to scaffold their learning during the direct instruction phase as well as interacting differently with the task at hand.

PERSPECTIVES

Faculty instructors are a limited resource in formal simulation-based training during post-graduate training. The rise of structured learning activities such as surgical boot camps and the emphasis on greater feedback and support for trainees means that instructor time is at a greater premium than ever before. Instructors must take time away from their busy clinical and workplace-based education activities in order to teach. Not only does this cost the healthcare system, the time commitment can reduce willingness to participate in education. Additional costs may be incurred by programs that must offer financial incentives for instructors. This trade-off between education and clinical work occurs in all academic postgraduate programs. Given the cost and investment required to recruit faculty for training, research is needed to maximize the efficiency of faculty involvement¹³. Our work directly contributes to this goal by identifying how instructor guidance is most helpful to trainees. Guided-discovery may be one approach to reducing the cost of training and instructor time in both post-graduate as well as pre-graduate learning courses¹⁸.

Post-graduate training also requires that trainees develop autonomy and are able to learn new skills or concepts effectively (Scholar role; Competency 1, Enabling 1.1, 1.2)^{19,20}. Further, Medical Expert^{19,20} (Competency 3, Enabling 3.1, 3.4) stresses trainees' abilities to transfer their training when faced with uncertainty and or complexity in future scenarios. Guided-discovery may be an effective organizing principle for educational design that can achieve these competencies across a wide range of disciplines and training environments. Our proposal would thus establish evidence of efficacy for guided-discovery for these competency roles.

4. Objective and Outcome Measure

Objective	Outcome measure
Primary outcome: To examine the effect of Guided-discovery-learning on far transfer of simple surgical skills	Difference in the two groups OSATS-scores on a far-transfer test evaluated by blinded raters
Secondary outcome: To examine the effect of Guided-discovery-learning on near-transfer of simple surgical skills To examine the primary learning-efficiency of the two types of teaching. To examine the effects on the different types of transfer for the intervention and control groups.	Difference in the two groups OSATS-scores on a near-transfer test evaluated by blinded raters Difference in OSATS-scores between immediate post-test. Difference in OSATS-scores between near-transfer and far-transfer-tests.
Explorative outcomes: To examine the difference in interaction between students receiving Guided-discovery, and those that didn't. To examine the difference in student interaction and approach to the task.	Using whole-room angle video recordings to observe the student-teacher interactions. Using task-focused video recordings to observe student-task interaction.
To examine different explorative approaches for examining the mechanics behind Guided-discovery To examine how students experienced the training.	Using think aloud video-recordings for select students. Using focus group interviews

5. Study Design

The study is a randomized experimental study comparing guided-discovery-learning to traditional instructional learning. The study will be performed at CAMES, including n=64 pre-clinical students from the Medical Faculty of Copenhagen University. Part 1 of this study is an experimental design with two phases that will test the efficacy of guided discovery: Phase 1 will be a learning phase with the experimental manipulations, and Phase 2 will take place one week later and be outcome assessment for near- and far transfer. Part 2 of this study will be an observational analysis of films of a sub-set of participants in the DD and IP conditions in order to establish differences in learning behaviors

between both conditions and possible mechanisms for guided-discovery learning. The analysis will compare how participants interact with the task in each learning condition including documenting activities in each phase and interactions with instructors.

For *Phase 1*, participants will be enrolled and randomly allocated to either the DD or IP groups. Each group consists of 8 participants. Participants will be randomized and the method of teaching allocated on the date of teaching. This will ensure generalization and ease of statistical analysis. In the DD group, participants will be given an example of a completed simple interrupted suture and their own skin pad, and suturing kit. They will then attempt to replicate the suture using the equipment and their own knowledge over 30 minutes. During the same period of time, the IP group will be taught using an instructor. The instructor will provide two demonstrations and explanations of the simple interrupted suture following which the participants will attempt the suture individually on their own skin pads and suturing kit (see Appendix A for Instructor directions; modifications will be made by an experienced surgical instructor on our team ST). The instructor will be told to provide feedback and guidance to the participants as well as answer any questions that participants may have. After the initial time, the DD group will be paired with an instructor who will provide two demonstrations and explanations of the suture and then interact with participants as they attempt the suture. The IP group will practice the suture without any further instructor guidance. At the end of the teaching session, all participants will complete a post-test requiring them to complete two simple interrupted sutures. Afterwards participants willing will be interview in short focus-group interviews. This entire session is expected to last 2 hours including consent and setup time.

After a 1-week delay, participants will return for *Phase 2* for the tests of near- and far transfer. Each group will again be randomly allocated a transfer task. Two transfer tasks will be used in this study: To test Hypothesis 1, (the impact on transfer to future learning), participants will be taught the interrupted vertical mattress suture. To ensure equivalency of design and to prevent biasing in favor of one group, all participants will be taught didactically, which will involve viewing a 15-minute video designed by an expert surgeon on our team (ST) to teach the novel suturing task. Participants will then be given 20-30 minutes to practice the suture following which they will perform two vertical matrass sutures on a typical skin pad. To test Hypothesis 2 (the impact on transfer of learning to a more complex version of the initial task) participants will perform two simple interrupted sutures on a suturing pad representing in an abdominal simulator with the added contextual change of different instruments and suture. In both groups, participants willing, will afterwards be recorded for a ‘Think-Aloud’ interview, in which they describe their approach to the suturing task out-loud. This phase is expected to last 1.5 hours. (See Appendix B for flow chart). All the interviews, Focus and Think-Aloud, as well as the observational filming will be investigated further and expanded upon in a separate additional protocol, which focuses on the qualitative data.

Outcomes, Measures, and Data Collection

Transfer Tasks

We chose our transfer task based on transfer theory¹⁵ which stresses the spectrum of possible applications of learning. Transfer to a complex variation of the skill, in this case, the simulated organ tissue in an abdominal trainer, is expected to create significant contextual barriers for participants to successfully enact their mental representation of the simple interrupted suture¹⁶. Whilst also including different instruments and suture, the haptic feedback and force required to complete the task are significantly different from the previous learning while the essential schema for the suture is preserved. Similarly, the vertical mattress suturing task involves the fundamental skills of suturing which participants will have developed from prior learning but creates new motor and perceptual patterns which must be scaffolded and developed from the initial learning experience. It will also require participants to engage any learning using their own self-regulation and capacity^{11, 12}.

Blinded raters will evaluate participants' suturing performances using a 5-point global rating scale taken from the OSATS tool which has previously demonstrated high inter-rater reliability across multiple contexts and good evidence of association with changes in trainee skill¹⁷ (see Appendix C for scale). We will use a repeated measures analysis to account for the multiple attempts.

6. Participant identification

6.1 Study Participants

Participants will be students primarily at the Medical Faculty of Copenhagen University who haven't received surgical education yet. Eighty participants will be included split into two groups. Both groups will be taught, filmed and tested at CAMES.

6.2 Inclusion and exclusion criteria

Participants are students currently attending a Danish bachelor at a Medical Faculty and who are willing and consent to participation in the study. Participants who have received prior suturing education are excluded from participating in the study.

7. Study Procedures

7.1 Recruitment

Participants will be recruited from the Medical Faculty of Copenhagen University, Zealand, Denmark. Everyone recruited will be given an information leaflet. (Appendix D)

7.2 Informed Consent

Participants must personally sign and date the 'Informed Consent Form' (appendix E) before they can participate in the study. Both written and verbal versions of the consent form and Participants information will be presented to participants, including everything that is to happen to the participants throughout the study. This included the known side effects and risks, associated in participating in the study. It will be clearly stated, that the participants are under no obligations to complete the study, and can withdraw at any time, without giving a specific reason for their withdrawal. Participants will be allowed as much time, as they wish to consider the information. Written Informed Consent will then be obtained by means of participant dated signature and dated signature of the person who presented and obtained the Informed Consent. The person who obtained the consent must be suitably qualified and experienced and have been authorized to do so by the Chief/Principal Investigator. A copy of the signed Informed Consent will be given to the participant. The original signed form will be retained at the study site in a locked cupboard which only the chief investigator has access to.

7.3 Randomization

Randomization

The study is a double randomized study. Participants will be randomized using en-bloc randomization sequence in groups. After enrollment participants will be assigned a group and a date for teaching. And the groups will then be randomized, and assigned a teaching method, which will be revealed on the date of teaching. Each group will then again be randomized to either to a near-transfer or a far-transfer group for the second phase of the study.

Groups range from A through H, making 8 groups in total. All groups assigned an uneven number will be allocated the intervention, whereas groups assigned an even number will be allocated the control. Furthermore, the 4 groups in the control and the intervention will be randomly assigned to a new number. Groups assigned an uneven number will be allocated the near-transfer group, and groups assigned an even number will be allocated the far transfer group.

For the recording and rating of the test each participant will assigned an identification number (A_1, B_1 etc) which will correspond to an identification key-number in the video (eg. 18920, 32, 564). The conversion key will be stored by the principle investigator and only he will have access to it, thus allowing the raters to score the participants blinded.

All randomization will be done using www.random.org and disclosed by an external party.

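### Teaching method and transfer task are allocated to whole groups (2 v 2 groups for the primary far-transfer test), but the analysis and sample size treat students as independent

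*Combined protocol and SAP*

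**What the plan says.** **Allocation.** Section 7.3 describes three steps. Students are placed in groups ("Participants will be randomized using en-bloc randomization sequence in groups") and given a teaching date. Whole groups then receive a method ("And the groups will then be randomized, and assigned a teaching method, which will be revealed on the date of teaching"), four groups to guided discovery (DD) and four to instruction (IP). Finally, "Each group will then again be randomized to either to a near-transfer or a far-transfer group for the second phase of the study". Section 5 repeats the last step ("Each group will again be randomly allocated a transfer task") and gives the group size: "Each group consists of 8 participants".

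**Analysis.** Section 8.1 lists Student's t-test for every outcome. Its Analysis paragraph adds a univariate ANOVA for the vertical mattress suture (far transfer), a repeated MANOVA or similar for post-test and near transfer, and mixed models whose only random factor is the participant. Teaching group and teaching date appear in none of them.

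**Sample size.** Section 8.2 requires 13 per group for 80% power at alpha 0.05, raised to 16 for loss, 64 in total. It makes no allowance for clustering. The printed effect size is cut off and sidedness is not stated.

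**The concern.** When whole groups are allocated, the uncertainty in the treatment contrast includes variation between groups. Students taught in the same session share peers and the instructor's feedback and answers, so their scores may be alike for reasons unrelated to the method. A student-level t-test counts 32 independent observations where the allocation supplied four units. The participant random effect does not help: it covers repeated sutures by one student, not similarity between students taught together. At stake are the p-value for the primary outcome and the power claimed for it.

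**Working it through.** **Inputs.** From section 7.3: 8 groups, 4 per method, each set of four divided between near and far transfer. From section 5: 8 students per group. From section 8.2: 13 required and 16 recruited per group, alpha 0.05, power 80%. Assumed here: ICC of 0 to 0.20, total variance 1, two-sided test.

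**1. Layout.** 8 × 8 = 64 students. Each method-by-task cell holds 2 groups, 2 × 8 = 16 students, which matches the 16 per group in section 8.2. Far transfer is therefore 2 v 2 groups.

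**2. The plan's figure.** Because the effect size is truncated, 13 can only be solved backwards. Two independent samples of 13 with 80% power give g = 1.145 two-sided (1.004 one-sided). With 16 per arm, g = 1.145 gives 88% power by the student-level t-test. Raising 13 to 16 allows for loss of 1 − 13/16 = 18.75% and nothing else.

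**3. Effective sample size.** Design effect = 1 + (8 − 1) × ICC; effective n per arm = 16 / design effect. It equals 13 at ICC = (16/13 − 1)/7 = 0.033.

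**4. False positives.** The student-level t-test was simulated under no effect, 2 v 2 groups of 8, 200,000 trials per setting.

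| Assumed ICC | Design effect | Effective n per arm | Type I error |
|---|---|---|---|
| 0 | 1.00 | 16.0 | 5% |
| 0.01 | 1.07 | 15.0 | 6% |
| 0.05 | 1.35 | 11.9 | 9% |
| 0.10 | 1.70 | 9.4 | 14% |
| 0.20 | 2.40 | 6.7 | 22% |

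The post-test comparison (4 v 4 groups of 8) behaves almost identically: 5.8%, 9.2%, 13.6% and 21.3% at ICC 0.01, 0.05, 0.10 and 0.20.

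**5. Power of a group-level test.** The variance of a group mean is v = ICC + (1 − ICC)/m for m students per group. The standard error of the contrast is √(2v/k) with k groups per arm, and power comes from the noncentral t with noncentrality g / SE.

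Example at ICC 0.05, m = 8: v = 0.05 + 0.95/8 = 0.169. With k = 2, SE = 0.411 and noncentrality = 1.145/0.411 = 2.79. The critical value is 4.30 with 2 df (35% power) and 2.78 with 4 df (56%). The 4 df arise when the group variance is pooled over all eight groups, 8 groups less 4 cell means, assuming equal group variance on both tasks.

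| Layout and test, g = 1.145, no loss | ICC 0 | 0.05 | 0.10 | 0.20 |
|---|---|---|---|---|
| Planned, far-transfer groups only (2 df) | 43% | 35% | 30% | 23% |
| Planned, all 8 groups in the model (4 df) | 68% | 56% | 47% | 36% |
| All 8 groups take far transfer (6 df) | 97% | 90% | 83% | 69% |
| 4 near and 4 far within each group (6 df) | 77% | 71% | 66% | 57% |

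The group-level tests hold about 5% type I error throughout. With 13 of 16 retained, the last two rows become 92%, 85%, 78%, 66% and 66%, 62%, 58%, 52%.

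**6. The split without a group-level test.** The uncorrected t-test after a 4/4 split still has 5%, 7%, 9% and 12% false positives at ICC 0, 0.05, 0.10 and 0.20, so re-allocation alone does not cure the problem.

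**The case against.** The best defence is that the ICC may be close to zero. Students appear to be randomised into groups, which limits pre-existing similarity. One instructor teaches everyone in Phase 1, from the script in Appendix A. For far transfer, "all participants will be taught didactically, which will involve viewing a 15-minute video". Students work on their own skin pads, and videos are coded, "thus allowing the raters to score the participants blinded". At ICC 0.01 the inflation is under one percentage point. All of this stands, and the larger figures above are scenarios, not estimates. It does not remove correlation that arises within the session from peers, feedback and answers. Nor could the far-transfer groups alone show that it is absent: at a true ICC of 0.05, their estimated group variance is zero or negative in about half of trials. The post-test, with 4 v 4 groups, would say somewhat more.

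Section 5 could also be read as allocating individuals, since it speaks of participants being randomly allocated to DD or IP. It goes on to say that the method is allocated on the teaching date, and section 7.3, the specific text, allocates groups.

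Two stronger readings are tempting and should be resisted:

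- A reader might infer that any correlation inflates the error. Only positive correlation does. Eight students competing for one instructor's attention could be negatively correlated, and the test would then be conservative.
- A reader might infer that no analysis can rescue the planned layout, so that the allocation must change. A group-level test restores the 5% level as the trial stands. Using all eight groups, as the near/far mixed model already planned in section 8.1 would do once given a group term, yields 4 df and not only 2. What analysis cannot restore is the power.

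**Conclusion.** The mismatch between unit of allocation and unit of analysis is real and affects the primary outcome. Section 8.1 should not stand as written. The size is unknown because the documents give no ICC: there is no inflation at ICC 0, and false positives rise to about 9% at 0.05 and 22% at 0.20. The 16 students per arm are worth fewer than the required 13 once the ICC exceeds 0.033.

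The documents do not support a claim that the test is certainly invalid, or that re-allocation is the only repair. The power figures rest on the back-solved two-sided g of 1.145, on 64 students and, for 4 df, on equal group variance on the two tasks. The total is itself inconsistent: the Synopsis and sections 5 and 8.2 say 64, section 6.1 says eighty, and the latter would change the number or size of groups.

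**What to change.** 1. **Section 8.1.** Analyse the primary outcome at group level, either by comparing teaching-group means or by a model with a random intercept for groups A–H and small-sample degrees of freedom. In the planned layout, use all eight groups for 4 df and state the equal-variance assumption. If the random-intercept model is chosen, say what happens when the group variance is estimated as zero; a comparison of means needs no such rule. *Cost:* text only, but the honest power at ICC 0 is 68% (4 df) or 43% (2 df), against 88% for the planned t-test.

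2. **Section 8.2.** State the effect size and sidedness, reconcile 64 with eighty, and restate power over an assumed ICC range such as 0 to 0.20, with the loss allowance. *Cost:* none.

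3. **Section 7.3, a design option before allocation, with no extra students.** Each version needs the group-level test.
   - All eight groups take the far-transfer test, with the test order fixed in the protocol. This has the higher power. *Cost:* possible order effects, and a longer Phase 2 session if near transfer is also tested; section 5 currently says "This phase is expected to last 1.5 hours".
   - Randomise four students to near and four to far transfer within each group. *Cost:* both tasks run in every session, near-transfer students must be kept from the video, and power stays below 80% even at ICC 0.

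4. **Section 7.3, pairing.** State whether DD and IP groups are taught in paired sessions. Section 5 has IP instruction running while DD students explore, which suggests that they may be. If so, the analysis should account for the pairing. *Cost:* one sentence, and possibly fewer degrees of freedom.
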